### **6.2 Planned recruitment rate**

Participants from our proposed NHS Trusts / Health Boards will be recruited over an estimated 29-month window across six sites with high levels of diversity and social adversity. Our target is to recruit approximately 6.5 participants consented per month, per site.

### **6.2.1 Risk of selection bias**

We will ensure that the cohort is sufficiently representative of our target group (people across the UK with experience of psychosis) so that the risk prediction algorithm is broadly applicable. The multi-site nature of the cohort will ensure heterogeneity of clinical response and varied socio-demographic characteristics, increasing the opportunity to develop a robust model in the context of care as usual. We will regularly review the socio-demographics of the cohort and adopt a more purposive sampling recruitment strategy if we observe a socio-demographic bias in our sample. Additionally, if we identify over- or under-represented groups within our dataset (relative to the target population), then we can apply weighting methods to all models.

### **6.2.2 Attrition**

We acknowledge that there might be some level of loss-to-follow-up. We will monitor attrition closely. In our previous digital psychosis trials, dropout rates have been low (e.g. retention rate in EMPOWER at 12-months of 85%; and 84% in Actissist 2.0 at 6-month follow-up). We will use evidence-based strategies to maximise retention and minimise loss to follow-up (see section 5.9, Engagement). In the case of large attrition, we can still build a risk prediction algorithm; however, we may need to build an algorithm based on fewer predictors (e.g. 4 - 6 instead of 5 - 7). Nonetheless, attrition is of direct interest for the adaptive sampling algorithm part of the study as we would like to know what predicts attrition and then incorporate this knowledge in an adaptive sampling algorithm to mitigate attrition in future DRM studies. Our primary outcome (relapse) should be available for almost all participants as we will be able to access medical records, which will document this outcome.

## **6.3 Procedure(s) to account for missing or spurious data**

For partially missing data (i.e. a subject has completed a questionnaire but has not completed all elements of that questionnaire), we will be using validated instruments and will follow the established procedures for calculating overall scores in the presence of partially missing data.

When data are completely missing for a whole questionnaire, we will record the occurrences of this, and use multiple imputation assuming these data are missing at random. The same approach will be used for all other occurrences of missing data, e.g., in the passively sampled data. We will also investigate appropriate sensitivity type analyses if we think these data may be informatively missing i.e., missing not at random, to see whether our findings are robust to these missing data.

Maximising follow-up and preventing missing data is of direct interest in the adaptive sampling methods. Therefore, this study will not take specific measures to prevent missing data, but we will learn from the missing data patterns to inform design of future studies in this regard.

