## 5.8 Study assessments

### 5.8.1 Active Symptom Monitoring (ASM)

Our existing ASM app has been developed through consultation and testing with people using services, and mental health professionals. We will continue to include lived experience involvement to develop the CONNECT app and the ASM item set.

Participants will be asked to complete a series of short assessments throughout the course of the study, administered via the CONNECT app, which contains a set of configurable items reflecting domains including psychotic symptoms, mood, anxiety, self-esteem, connectedness to others, fear of relapse. Items include both positive (e.g. 'I've been feeling close to others') and negative (e.g. 'I've been worrying about relapse') content. This will provide real-time self-reported information about these clinical domains. Each item is completed using a simple screen swipe, which enables quick and efficient completion by users. Each item is automatically scored on a Likert scale. Where particular items score over a certain threshold, users are invited to complete supplementary questions to enable more fine-grained assessment of that domain. Variability of psychotic symptoms will be measured via the validated *ClinTouch* psychotic symptom item set within the app. We will also include items about a person's whereabouts (e.g. work, home) and who they are with (e.g. alone, with a significant other, with others more generally) to contextualise data.

The CONNECT app will deliver an auditory and visual notification on the participant's home screen between 4pm and 9pm. Participants will have until midnight to respond to notifications. They will also be able to self-initiate use at any time, but will only be able to complete the questions once per day. Data are wirelessly uploaded in real-time to the secure cloud-hosting with AWS supported by a UoM-approved IT supplier. We will include the ability to configure the app in the event a participant is comfortable with using some aspects of the software system (e.g. ASM), but not others (e.g. passive sensor monitoring; wearable device).

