[figure not shown]

Figure 4. Nested study examining utility of different types of wearable device

research objectives. However, the Fitbit did not demonstrate non-inferiority compared to the Apple watch. Therefore, the Apple watch was retained due to its high acceptability and uptake among participants, and the additional metrics available over and above the Fitbit in meeting the study's research objectives. As this is a nested study, the dataset gathered from pilot participants will form part of the main cohort dataset.

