##### Participants with Android Phones:

- Will be offered a Fitbit, as it is the only compatible wearable device for Android users.
- Participants who already own a Fitbit may continue using their existing device.

This approach minimises the need for participants to carry two phones and ensures seamless integration of wearable data with their respective smartphones.

Participants who enrolled during the pilot phase or the interim period while awaiting ethical approval for revised study procedures, and are using a Samsung smartwatch, may continue using the Samsung smartwatch for the study duration and keep it, but they will be encouraged to switch to a Fitbit, the only remaining compatible device for Android phones, for the remainder of the study.

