We will develop the risk prediction algorithm using Group 1 ( $n = 800$ ), which will then be validated and refined as needed in Group 2 ( $n = 300$ ). Under the assumption that data will be missing at random, multiple imputation will be applied for covariates, any covariates with over 60% missingness will be excluded in the interests of clinical utility (see Section 6.3). The primary outcome will be the binary indication of relapse in either, for example, 7 days (model 1) or 28 days (model 2) from time-of-prediction. For an individual participant, such outcomes will be defined in a 'rolling manner', where we define outcomes at the end of each week (model 1) or each month (model 2). To achieve the best performing model, we will consider a range of analytical models, including (but not limited to): logistic regression, artificial neural networks, support vector machines, random forests, hidden Markov models, and Bayesian approaches. For example, the hidden Markov models will use certain features of an individual's inputs (ASM and PSM) and use the data to calculate for each individual a risk of being in one of a small number of mutually exclusive 'states' which correspond to, for example, remission, deteriorating, relapse. The data will also allow a day-to-day calculation of instability ('entropy') – the likelihood of remaining in that state (Figure 5). Individuals can 'switch' between states. We will include interactions between predictors to allow certain subgroups of individuals to have slightly different 'versions' of the algorithm; that is, tailor the model to subgroups across the heterogeneous target population.

[figure not shown]

Figure 5. Graphical representation of algorithm functionality

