An essential aim of this project is to determine the feasibility and acceptability of long-term engagement with AMS. By choosing aesthetically appealing, commercially marketed fitness trackers, and by incorporating feedback from our Involvement groups, we hope to minimise stigma and burden for the user and maximise acceptability. However, there may be several factors affecting willingness to use the devices. Participants will be asked to wear the device on their non-dominant wrist for 24 hours a day, ideally taking off only to shower and charge. All devices will be non-invasive, painless, and extremely low risk. They are similar in size and dimension to a watch, manufactured primarily in rubber, and are marked as lifestyle devices, therefore not denoting participation in a research study, reducing stigmatisation and eliminating the possibility of identifying an individual as a research participant. They have been thoroughly tested and approved for safety by regulatory authorities. Participants may however find them to be uncomfortable or cumbersome. They may forget to charge them, or not know how to charge them. The introductory training provided for all participants will mitigate this risk, along with provision of a 'help' section in the smartphone app, and the availability of contact with the research team. The extent to which participants continue to wear the device, or complete the questionnaires on the CONNECT smartphone app is likely to correlate with their mental health; a decline in mood may show itself through disengagement with the research protocol. Regular review of the data by the research team, alongside practices designed to encourage engagement, may help to identify whether a loss of data is due to potential relapse, or technical/practical issues which can be resolved.

The questionnaires to be completed on the CONNECT app have been well-tested in pilot studies and in other research protocols, however the frequency of assessment and usability of the app may make completion of the questionnaires difficult. A member of the research team will contact the participant once a week for the first 4 weeks, followed by monthly contact (e.g. phone call, text message), to mitigate this risk.

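### Sections 6.3 and 6.4.2 impute every app and sensor gap as missing at random and drop covariates over 60% missing, although section 9.1.2 expects gaps to track mental health; gaps are not named as predictors, nor structural blanks separated

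*Protocol*

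**What the plan says.** Section 6.3 takes a wholly missing questionnaire first: the plan is to "use multiple imputation assuming these data are missing at random". It then generalises: "The same approach will be used for all other occurrences of missing data, e.g., in the passively sampled data". The next sentence allows sensitivity analyses if the team comes to think the data are informatively missing. No method is named.

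Section 6.4.2 repeats the missing-at-random assumption for covariates and adds a cut-off: "any covariates with over 60% missingness will be excluded in the interests of clinical utility". It describes likely candidate predictors as aggregates of active and passive observations over a past window, plus demographics.

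Section 9.1.2 says that wearing the device and completing the app are likely to correlate with mental health, and that "a decline in mood may show itself through disengagement with the research protocol". It adds that reviewing the data may show whether lost data reflect a potential relapse or a technical problem.

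Several blanks arise by design:

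- **Section 5.8.1:** "Where particular items score over a certain threshold, users are invited to complete supplementary questions". The item set is also personalised and altered during follow-up, and a participant may use the app without sensors or wearable.
- **Section 5.8.2:** any passive stream can be switched on or off by the participant.
- **Section 5.8.2.2, on Android users:** "Will be offered a Fitbit, as it is the only compatible wearable device for Android users".
- **Section 5.8.2.1:** the Apple Watch was kept partly for "the additional metrics available over and above the Fitbit".
- **Section 5.9:** prompts can be paused.

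**The concern.** The protocol names loss of data as a possible sign of relapse, and then prescribes handling for lost data that does not itself use that sign. Multiple imputation supplies plausible values for the missing observations. It does not carry the fact that they were missing into the prediction model unless that fact is made a covariate. Non-response is modelled in section 6.4.3, but as an outcome of the engagement models, and section 6.3 says the missing-data patterns will inform future studies. Nothing makes non-response or non-wear a candidate predictor of relapse.

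The second strand is structural. A supplementary question that was never shown, or an Apple Watch metric in a Fitbit wearer, has no underlying value to recover. The rules make no exception for these, so they would be imputed, or would count toward exclusion at 60%.

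At stake is the primary aim: the discrimination of the relapse model, and whether performance in Group 2 reflects what could be achieved at the moment of prediction.

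**Working it through.** The protocol gives no missingness figure to reproduce; the 60% cut-off is a rule, not a result. Two checks are possible, both resting on assumed rates.

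**1. Does the gap add anything once imputation is done properly?**

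Input from the protocol: within-person correlation 0.52 (section 6.1). Assumed: seven daily prompts per week, a symptom shift of 0.8 SD before relapse, 2% of rows with an event, and missed prompts varying between people (beta-binomial, concentration 3). For scale, 25% relapse a year over 13 windows of 28 days is 0.25/13 = 1.9% per window.

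Three logistic models were compared by AUC: the weekly symptom mean with gaps set to a typical value; the same mean with gaps filled conditionally on that week's observed days; and the second model plus the count of missed prompts.

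| Missed: ordinary vs pre-relapse week | Typical-value fill | Conditional fill | Conditional fill + count | Gain from count |
|---|---|---|---|---|
| Equal | 0.75–0.76 | 0.75–0.76 | 0.75–0.76 | none |
| 25% vs 35% | 0.73 | 0.75 | 0.77 | 0.77 − 0.75 = 0.02 |
| 25% vs 45% | 0.71 | 0.735 | 0.80 | 0.80 − 0.735 = 0.065 |
| 30% vs 60% | 0.67 | 0.705 | 0.83 | 0.83 − 0.705 = 0.125 |

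Two things follow. Typical-value fill exaggerates the harm of imputation: at 25% vs 45%, conditional fill recovers 0.735 − 0.71 = 0.025. But the count still adds 0.02 to about 0.13 on top of conditional fill whenever missingness rises before relapse, and nothing when it does not.

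A second simulation imputed a single feature (shift 0.5 SD) by multiple imputation from a correlated baseline covariate. AUC without and with a missingness indicator was 0.59 and 0.66 (30% vs 50% missing), 0.56 and 0.73 (30% vs 70%), and 0.62 and 0.62 (30% in both). Using the outcome in the training imputation did not help, because the outcome is unknown when predicting.

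**2. When would the 60% rule remove a device-specific metric?**

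Overall missingness = 1 − (device share × completeness within that device). The metric is excluded when this exceeds 0.60, that is, when share × completeness < 0.40.

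Section 1.4 cites 69% to 88% compliance with app assessments, used here as a proxy for wearable completeness:

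- completeness 69%: excluded if share < 0.40/0.69 = 58%
- completeness 88%: excluded if share < 0.40/0.88 = 45%
- completeness 100%: excluded if share < 40%

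The device split is not stated, so whether any Apple-only metric would be excluded cannot be determined.

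**The case against.** Much of the case on the other side stands.

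- **Correlation with mental state does not by itself break missing at random.** The assumption conditions on observed data: earlier answers, the remaining days, sensors and clinical measures. Multiple imputation is also not mean fill. Both points hold, and the table shows that conditional fill recovers part of the loss.
- **The candidate list is open.** Section 6.4.2 says what predictors will likely be, and app use is recorded continuously. Engagement features could still be added, so a reader might infer that relapse signal will be imputed away, but the text does not support that. It supports only that nothing requires such features.
- **The direction is not settled.** Section 6.4.3 foresees stable, low symptoms leading to disengagement, the opposite of section 9.1.2. The net effect could be small, and the simulated gain reflects a differential that was put in by assumption.
- **Other tempting inferences are also unsupported.** The protocol does not say that imputation will use outcomes or later data. It gives no trigger rate or device split from which to conclude that branch items or Apple metrics will be dropped, and the core item that triggers a branch remains observed.
- **The 60% rule has a stated purpose, clinical utility.** A metric that most users cannot supply is of limited use in a general tool. That purpose should be kept.
- **Detail may belong in the SAP.** Section 6.4 is a summary to be expanded. But the imputation and 60% rules are already stated without exception, and a SAP that follows them inherits the problem.

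The foreseen sensitivity analysis does not answer the point. It is conditional, and it tests robustness without bringing missingness into the model.

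**Conclusion.** The point holds as an internal tension with a cheap remedy. Sections 6.3 and 6.4.2 fix a missing-at-random rule for all gaps, and section 9.1.2 gives reason to treat some gaps as information about relapse. As written, the model need not use that information, and blanks that are not lost values fall under the same two rules.

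The size of any loss is unknown. Under the assumed rates, a missed-prompt count adds about 0.02 to 0.13 in AUC beyond conditional imputation when missingness rises before relapse, and nothing when it does not. These figures rest on assumed missingness rates, an assumed symptom shift and worsening as the driver of disengagement; none is a trial estimate. Possible exclusion of device-specific metrics depends on an unstated device share.

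This should be fixed but is not critical: the data are unaffected and nothing irreversible has been set.

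**What to change.** (a) In section 6.4.2, name the recent missed-prompt count and non-wear time as candidate predictors, subject to the same penalised selection as the others.

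(b) In section 6.3, state that gaps in predictors are filled using only data available at the prediction time, by the same rule in Group 1 and Group 2, and without the outcome when predicting.

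(c) Code untriggered, unasked or device-unavailable items as not applicable instead of imputing them. Compute the 60% figure among person-time in which the item could have been recorded. Report separately the share of participants who can supply it, so that the clinical-utility aim is still served.

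The cost is protocol or SAP wording and analysis programming, with no new data collection. The downside is that one or two engagement features compete for the 5–7 predictors that section 6.1 says the sample supports (4–6 under large attrition, section 6.2.2). Device-specific sub-models are not required, and would split the 800 participants in Group 1.

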## **6.4 Statistical analysis plan**

Statistical analyses are required for the study research questions. We provide a summary of our statistical analysis plans (SAP) below, which will be expanded into a detailed SAP upon project start (published on open-access repositories: the open science framework).

### **6.4.1 Identification of prognostic variables (Research question 1)**

We will use descriptive statistics and unsupervised machine learning techniques to identify individual variables, and sets of variables, that are most predictive of relapse. Simple or low fidelity/dimension

variables will be analysed in simple regression models to calculate their association with relapse outcomes. High fidelity variables (such as passively collected data from phones) will first be passed through machine learning algorithms such as autoencoders to reduce their dimensionality, then tested for association with relapse. Promising variables will be identified, summarised and passed forward to predictive algorithm development. To be clear, as per best-practice, all identification of prognostic variables will be based on multivariable analyses: we will not use results from univariable analysis to inform predictor selection for the risk model development (which would be a sub-optimal approach).

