#### **6.4.2 Developing a prediction algorithm (Research question 2)**

We will follow best-practice guidelines in the development of risk prediction algorithms (Collins, et al., 2015) and will report findings according to the TRIPOD statement (Spitzer RL, 2006) and the guidelines for developing and reporting machine learning predictive models in biomedical research (Luo, et al., 2016). We will adopt an agile approach to algorithm development that will be responsive to data as it accrues and to evolving algorithm performance. As we do not know in advance which combination of predictors and analytical method will be most effective, we will employ the following strategy that enables us to systematically explore the combinations. When we have enough data to begin algorithm development, the data scientists, clinical experts, in consultation with advisory group members, will identify a list of candidate predictors (ready for variable selection using the data) and corresponding methods to develop the initial algorithms; research question 3 will inform discussions of candidate predictors. These will be deployed into the model development sandbox.

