Repeated measures for an individual will be appropriately accounted for in any models (e.g. random effects at the participant-level, or use of landmarking techniques). We will use a data-driven approach to select predictors for inclusion in the final risk prediction algorithm. This variable selection procedure will choose from a pre-defined list of candidate predictors (as defined above). For example, candidate predictors will likely be an aggregate of various actively and passively collected observations over a historical time-window as well as demographic variables. For regression-based models (e.g. logistic regression), we will perform variable selection using penalised maximum likelihood (e.g. LASSO L1-regularization), while variable selection is inherent to the machine-learning methods. The use of penalised regression will also help mitigate against overfitting (Riley, et al., 2019).

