Internal k-fold cross validation within Group 1 will be used to validate the models, doing this at key landmark times to account for the dynamic (time-updated) nature of an individual's risk estimate. Here, we will quantify predictive performance using calibration (agreement between the observed and expected event proportion, across the full risk range) and discrimination (ability of the algorithm to separate those who have the event from those that do not). For discrimination, we will calculate sensitivity, specificity, positive and negative predictive values at clinically relevant cut-off points, and area under the receiver operating characteristic curve (AUC/C-statistic). For calibration, we will produce estimates of calibration-in-the-large, calibration slope and flexible calibration plots (Van Calster, et al., 2016). The internal validation results will be used to select between the analytical methods (i.e., logistic regression, artificial neural networks, support vector machines, random forests, hidden Markov models, and Bayesian approaches) for each model (i.e. for both models 1 and 2). The primary criteria for algorithm performance will be high specificity (valued by services), with sensitivity a secondary criterion (i.e. we want to maximise specificity whilst ensuring clinically useful sensitivity). This approach to algorithm development on real-time data also offers the potential to be able to stop data collection should an algorithm be developed that meets the requirements for sensitivity and specificity and meets the minimum sample size criteria. The specific requirements for an acceptable level of sensitivity and specificity is a central topic of investigation in this project; we will target performance that is not only statistically significant, but is also acceptable to end-users, clinicians and other stakeholders to maximise clinical utility of the model (i.e. we will establish this iteratively through our PPI and qualitative work).

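### Section 6.4.1 passes relapse-screened variables into the model while section 6.4.2 calls the candidate list pre-defined; if the screen is run once on Group 1 before cross-validation, internal performance will be optimistic

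*Protocol*

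**What the plan says.** Section 6.4.1 of the protocol describes a screening step that uses the outcome. Low-dimension "variables will be analysed in simple regression models to calculate their association with relapse outcomes". High-dimension sensor data go through autoencoders "to reduce their dimensionality, then tested for association with relapse". The step ends: "Promising variables will be identified, summarised and passed forward to predictive algorithm development". A clarification follows: "all identification of prognostic variables will be based on multivariable analyses", and "we will not use results from univariable analysis to inform predictor selection for the risk model development".

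Section 6.4.2 describes another origin for the candidates. Once enough data have accrued, data scientists and clinical experts, consulting advisory group members, "will identify a list of candidate predictors (ready for variable selection using the data"). It names research question 3 as informing that discussion. Research question 3 (section 3.3) concerns usability, acceptability and adherence; the screening in 6.4.1 belongs to research question 1. Later in 6.4.2: "This variable selection procedure will choose from a pre-defined list of candidate predictors (as defined above"), by LASSO for regression models and by built-in selection for machine-learning methods.

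On validation, 6.4.2 says: "Internal k-fold cross validation within Group 1 will be used to validate the models". The results choose between the analytical methods for each horizon. The same paragraph raises the possibility of stopping data collection once an algorithm meets the sensitivity and specificity requirements and the minimum sample size.

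**The concern.** A reader cannot tell whether relapse data decide what gets onto the candidate list. Under 6.4.1 they do; under 6.4.2 the list comes from expert discussion and is fixed before selection starts.

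The difference matters because of the order of the steps. Cross-validation gives an honest estimate only if every step that looks at the outcome is repeated within each training fold. A screen run once on all of Group 1 lets the held-out participants influence which predictors survive, and those participants are then used to judge the model. This applies to a multivariable screen as much as to a univariable one, since both use the held-out outcomes. A step in which people identify and summarise promising variables is also hard to repeat fold by fold unless that is planned.

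At stake are the internal AUC, sensitivity and specificity that feed the choice among six families of method, and possibly a decision to stop collecting data. Group 2 is recruited last (section 4.1), so an early stop could shrink the set that would reveal the optimism.

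**Working it through.** The protocol gives no figure for this optimism, so there is none to reproduce. The check has two parts.

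**1. The order of steps as written**

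- 6.4.1: test against relapse, then pass the promising variables forward.
- 6.4.2: experts list the candidates; the list is called pre-defined; penalised or built-in selection follows.
- 6.4.2: k-fold cross-validation of the models within Group 1.

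The protocol does not say that the 6.4.1 screen is repeated inside the folds. It does not say which records the screen uses. It does not say how the output of 6.4.1 relates to the experts' list.

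**2. Simulation of a multivariable screen outside and inside the folds**

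Inputs from the protocol: 800 development and 300 validation participants, and relapse of 25% or 40% in 12 months (section 6.1).

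Assumptions: K independent standard-normal features; 7 retained (the upper end of the 5 to 7 predictors in section 6.1); 10 folds; one record per participant. In the signal case there are 5 true predictors, each with a log-odds of 0.33 per SD. There were 40 datasets per setting, and 12 where K = 1000.

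Method: multivariable forward selection of 7 features against relapse, then logistic regression. Selection was done either once on all 800 or again within each training fold. Excess = cross-validated AUC (screen outside folds) minus cross-validated AUC (screen inside folds). The Group 2 column is the AUC in the 300 held-out participants.

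With real signal:

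| Relapse | K | Outside | Inside | Excess | Group 2 |
|---|---|---|---|---|---|
| 25% | 20 | 0.685 | 0.672 | 0.013 | 0.681 |
| 25% | 50 | 0.695 | 0.667 | 0.028 | 0.667 |
| 25% | 200 | 0.698 | 0.647 | 0.051 | 0.658 |
| 25% | 1000 | 0.712 | 0.632 | 0.080 | 0.629 |
| 40% | 20 | 0.692 | 0.682 | 0.010 | 0.679 |
| 40% | 50 | 0.688 | 0.668 | 0.020 | 0.671 |
| 40% | 200 | 0.700 | 0.668 | 0.032 | 0.666 |
| 40% | 1000 | 0.704 | 0.641 | 0.063 | 0.653 |

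With no signal and 25% relapse, where the true AUC is 0.50:

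| K | Outside | Inside | Excess |
|---|---|---|---|
| 20 | 0.555 | 0.499 | 0.056 |
| 50 | 0.585 | 0.491 | 0.094 |
| 200 | 0.629 | 0.496 | 0.133 |
| 1000 | 0.667 | 0.498 | 0.169 |

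The excess grows with the number of features screened. Screening inside the folds removes it, and the nested value lies close to the Group 2 value. At 25% relapse with signal, the outside figure rises from 0.685 to 0.712 as noise features are added, while the Group 2 figure falls from 0.681 to 0.629.

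Only AUC was simulated. Cross-validated sensitivity and specificity are exposed to the same mechanism, but no size is given for them.

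**The case against.** The strongest reply is that the protocol never says the screen sits outside the folds. Section 6.4 presents itself as a summary to be expanded in a detailed SAP, 6.4.2 commits to best-practice guidance for prediction and machine-learning models, and nesting is the kind of detail a SAP settles. Pre-defined may simply mean fixed before the penalised selection, with the experts' list as the thing defined above. This stands in part: inflation cannot be stated as a fact. It does not remove the conflict between the two accounts of where candidates come from, which the protocol itself states. A list fixed before the LASSO may still have been filtered on relapse.

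Four stronger readings are tempting and not supported:

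- **That univariable screening decides what enters the model.** Section 6.4.1 bars this expressly, despite the sentence on simple regressions.
- **That the wrong method will be chosen.** Optimism shared by all methods raises absolute figures without necessarily changing their order. No comparison between methods was run.
- **That the final performance estimates are biased.** Section 6.4.4 takes these from Group 2, which this mechanism does not touch provided Group 2 is kept out of the screening and of any refinement before it is used.
- **That the inflation is large.** With 20 features and real signal it is about 0.01. The protocol does not say how many features will be screened.

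The simulation is also simpler than the study: it uses one record per participant and independent features, whereas 6.4.2 defines rolling weekly or monthly outcomes.

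**Conclusion.** The point holds in conditional form. Sections 6.4.1 and 6.4.2 give two unreconciled routes to the candidate list. If the written order is followed with Group 1 records and the screen is not repeated within folds, the internal performance figures will be optimistic even though the screen is multivariable. At 25% relapse with real signal, the excess in AUC is about 0.01, 0.03, 0.05 and 0.08 for 20, 50, 200 and 1000 screened features; at 40% it is about 0.01, 0.02, 0.03 and 0.06. These sizes rest on the assumed feature counts, 7 retained predictors, 10 folds, the chosen signal strength and one record per participant. The consequence is confined to internal validation, the absolute level on which a method is judged, and any decision to stop data collection on performance.

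**What to change.** Reconcile sections 6.4.1 and 6.4.2 into one rule, by either of two routes:

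- **List fixed without the outcome.** Use the expert and advisory-group route already in 6.4.2, with dimension reduction that does not see relapse. Report the 6.4.1 associations as descriptive answers to research question 1 and remove the sentence that passes them forward.
- **Outcome-based screening kept.** State that the whole screen, including the autoencoder fit, is repeated inside each training fold of Group 1, with folds formed by participant so that one person's records never fall on both sides. The screen then has to be an algorithm that can be rerun, not a judgement made once.

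Under either route, state that Group 2 records take no part in the screening.

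The cost is protocol wording and, for the second route, more computing. No new data are needed. The internal performance figures will look less favourable.
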